9.4 Additional Efficacy Endpoints and Analyses

9.4.1 Additional Efficacy Endpoints

The additional efficacy endpoints for Part 1 and Part 2 are defined in Section 3.2.

The additional efficacy endpoints will be analyzed based on the AO approach. Descriptive statistics will be provided for continuous (mean, median, standard deviation, standard error, minimum, and maximum) and categorical (count, percentage) efficacy endpoints.

9.5 Efficacy Subgroup Analyses

The following subgroup analyses will be conducted for the key efficacy endpoints. Descriptive statistics (number and percentage) will be provided.

- Age (6 - < 12, 12 - 24 months)

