The key efficacy endpoints will be summarized descriptively for age groups from 6-months to less than 1 year and 1 year to 2 years of age.

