3.0 Endpoints

3.1 Key Efficacy Endpoints for Part 1 and Part 2

The key efficacy endpoints for Part 1 and Part 2 are:

- The change from baseline in 4-week overall SBM frequency rate (SBMs/week) during the Study Intervention Period
- The change from baseline in 4-week stool consistency (Bristol Stool Form Scale) reported by LAR/parent/guardian/caregiver during the Study Intervention Period
- The change from baseline in 4-week straining reported by LAR/parent/guardian/caregiver during the Study Intervention Period

The details of the derivation of these efficacy endpoints are provided in [Appendix B](#).

The estimands corresponding to the efficacy endpoints are the mean change from baseline in overall SBM frequency rate, stool consistency, and straining during the study intervention period, regardless of interruption of study drug and without use of rescue medications in the linaclotide and placebo groups in the intent-to-treat (ITT) population.

3.2 Additional Efficacy Endpoints for Part 1 and Part 2

The additional efficacy endpoints for Part 1 and Part 2 are:

- The achievement of no longer meeting modified Rome IV criteria for FC at the end of the 4-week study intervention period
- The global change in symptoms at each week during the study intervention period
- The global severity of symptoms at each week during the study intervention period

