9.3.2 Main Analysis of Key Efficacy Endpoints

The estimands corresponding to the key efficacy endpoints are the mean change from baseline in overall SBM frequency rate, stool consistency, and straining, regardless of interruption of study drug and without use of rescue medications in the linaclotide and placebo groups in the intent-to-treat (ITT) population.

The key efficacy endpoints will be analyzed based on the AO approach. Descriptive statistics (mean, median, standard deviation, standard error, minimum, and maximum) will be provided.

The attributes of the estimand corresponding to the key efficacy objectives are summarized in [Table 1](#).

Table 1. Summary of the Estimand Attributes Corresponding to the Key Efficacy Objectives

Attributes of the Estimand					
Estimand Label	Treatment	Endpoint	Population	Handling of Intercurrent Events	Statistical Summary
Key	Part 1: linaclotide Part 2: linaclotide or placebo (see Section 3.1)	Change from baseline in 4-week overall SBM frequency rate (SBMs/week) during the study intervention period	ITT	IE1: use of any rescue therapy for the treatment of FC IE2: premature discontinuation of study drug IE3: study drug interruption due to poor tolerability All data occurred on the day of or the day after IE1 will not be used. All data after IE2 will not be used. All data after IE3 will be used.	Mean change from baseline in 4-week overall SBM frequency rate (SBMs/week) during the study intervention period in linaclotide (Part 1), or linaclotide or placebo (Part 2)
Key	Part 1: linaclotide Part 2: linaclotide or placebo (see Section 3.1)	Change from baseline in 4-week stool consistency (Bristol Stool Form Scale) reported by LAR/parent/guar dian/caregiver during the study intervention period	ITT	IE1: use of any rescue therapy for the treatment of FC IE2: premature discontinuation of study drug IE3: study drug interruption due to poor tolerability All data occurred on the day of or the day after IE1 will not be used. All data after IE2 will not be used. All data after IE3 will be used.	Mean change from baseline in 4-week stool consistency reported by LAR/parent/ guardian/ caregiver during the study intervention period in linaclotide (Part 1), or linaclotide or placebo (Part 2)

Attributes of the Estimand					
Estimand Label	Treatment	Endpoint	Population	Handling of Intercurrent Events	Statistical Summary

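### SAP 9.5 prescribes counts and percentages for the age-subgroup summary of three continuous change-from-baseline endpoints

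*SAP*

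**What the plan says.** SAP 9.5 sets the scope of the subgroup analysis: "The following subgroup analyses will be conducted for the key efficacy endpoints". The only factor is age, in two levels: 6 to under 12 months, and 12 to 24 months. The statistics are then named: "Descriptive statistics (number and percentage) will be provided".

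SAP 3.1 lists three key efficacy endpoints. The first reads "The change from baseline in 4-week overall SBM frequency rate (SBMs/week) during the Study Intervention Period". The other two have the same form: one concerns the child's averaged Bristol stool-form score, the other the averaged straining score, both as recorded by the caregiver.

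For these same endpoints in the full population, the sentence on statistics in SAP 9.3.2 begins: "Descriptive statistics (mean, median, standard deviation, standard error, minimum, and maximum) will be". Protocol 7.4 lists the same statistics for the key endpoints and, under its subgroup sub-heading, adds: "The key efficacy endpoints will be summarized descriptively for age groups". It then names the two age bands.

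**The concern.** A count and a percentage describe a categorical outcome. A change in weekly SBM rate, or in an averaged stool-form or straining score, has no category to count unless a threshold is set, and none is. A programmer who follows SAP 9.5 to the letter can report only the number of children in each age band.

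The stake is completeness of the descriptive output. The study does no hypothesis testing, so descriptive summaries are its entire efficacy result, and age is the only efficacy subgroup planned. Followed literally, the age tables would not deliver the summary that Protocol 7.4 describes. The programmer would otherwise have to depart from the SAP without written authority.

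**Working it through.** The plan states no figure to reproduce here, so the check is a comparison of texts.

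1. **Type of the endpoints.** SAP Appendix B derives the SBM rate as observed SBMs divided by days, times 7. Stool consistency is the average of BSFS scores over caregiver-observed SBMs. Straining is the average of per-BM straining scores. A change from baseline in any of these is numeric. BSFS is ordinal for a single stool, but the analysed score is a per-child average, so its categories cannot be tabulated as the endpoint.

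2. **Is there a responder version?** None is defined in SAP 3.1, 9.3 or Appendix B, or in Protocol 3.2 or 7.4. The additional endpoints in SAP 3.2 (Rome IV status, global change, global severity) are recorded in categories and would suit counts and percentages. SAP 9.5 covers the key endpoints only.

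3. **What the rest of the plan prescribes.**

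| Place | Statistic |
|---|---|
| SAP 9.3.2 | mean, median, SD, SE, minimum, maximum for the key endpoints |
| SAP Table 1 | mean change from baseline for each key endpoint |
| SAP 9.4.1 | mean and related statistics for continuous endpoints; count and percentage for categorical ones |
| SAP 7.0 | number and percentage for categorical variables |
| Protocol 7.4 | mean, median, SD, SE, minimum, maximum; descriptive summary by age group |
| SAP 9.5 | number and percentage for the key endpoints by age group |

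SAP 9.5 is the only one that assigns counts and percentages to the key endpoints.

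4. **Is the difference declared?** SAP 14.1, the place for changes from the protocol's planned analyses, says not applicable. The departure from Protocol 7.4 is therefore not an announced change.

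5. **How much output is affected.** There are three Part 1 cohorts and two Part 2 arms, so 3 + 2 = 5 groups. Two age levels give 5 × 2 = 10 cells, and three endpoints give 10 × 3 = 30 summaries, before any pooled same-dose rows.

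6. **How large the cells are.** Full planned enrolment is 3 × 6 + 12 = 30 children, with 12 / 2 = 6 per Part 2 arm. The average is 30 / 10 = 3 children per cell. Pooling the selected dose across Parts 1 and 2 gives 6 + 6 = 12 children, or 6 per age group on average. The actual split by age is unknown, and some cells may hold one child or none. For consistency and straining the number can be smaller still, because SAP 9.1 excludes children with no caregiver-observed SBM at baseline. With n = 1 neither an SD nor an SE can be computed.

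**The case against.** The best reply is that the intended statistic is easy to find. SAP 9.5 refers to the key efficacy endpoints, whose summary is fixed as a mean change in SAP 9.3.2 and Table 1. SAP 9.4.1, immediately before it, keeps counts and percentages for categorical endpoints. Protocol 7.4 lists the right statistics and the age subgroup under one heading, and SAP 14.1 declares no departure from it. A sensible programmer would see the slip and produce means.

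This stands as evidence of intent, and it limits the harm. It does not remove the error: the parenthetical in SAP 9.5 is the only instruction in the SAP on subgroup statistics, it is explicit, and no other SAP sentence overrides it.

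It is also fair to say that little depends on these tables. The sample size is not statistically driven, the dose-selection criteria in Protocol 4.1 do not use age-group efficacy, and the cells are tiny.

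Two stronger readings are tempting, and the documents support neither:

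- A reader might infer that the plan loses an estimate of a subgroup treatment effect. No such estimate was planned. There is no formal hypothesis and no testing, and SAP Table 1 specifies no between-group contrast even for the main analysis. Only the summary of change within each age group is affected.
- A reader might infer that the design guarantees children under 12 months in every Part 1 cohort, so that results for them would be collected and then not reported. The enrolment rule is at least one child aged 12 months or less per Part 1 cohort, while the younger subgroup is under 12 months. A child aged exactly 12 months meets the rule and falls in the older group. The documents give no such minimum for Part 2.

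**Conclusion.** The point holds as an internal contradiction. SAP 9.5 names a statistic that does not fit the endpoints it covers, and it disagrees with SAP 9.3.2, Table 1 and 9.4.1 and with Protocol 7.4. On a literal reading, all three key endpoints in both age groups lack a summary of change.

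It is most likely a drafting slip, and its weight is low: it alters no trial conduct, no main result and no decision rule. The average of three children per cell assumes full planned enrolment of 30; the protocol allows as few as 18. The conclusion itself depends only on the wording of the two documents.

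**What to change.** Replace the statistics sentence in SAP 9.5 with:

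> n, mean, median, standard deviation, standard error, minimum and maximum of the change from baseline will be provided by age group within each cohort (Part 1) and treatment group (Part 2), and for pooled same-dose groups as in Section 9.1; where n = 1 only the observed value is shown.

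This brings SAP 9.5 into line with SAP 9.1 and 9.3.2 and with Protocol 7.4, and it settles the one-child cell in advance. The cost is one sentence in the SAP. No new data and no protocol amendment are needed, and the change is best made before the tables are programmed.

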10.0 Safety Analyses

10.1 General Considerations

Safety analyses will be performed on the safety analysis population in the 4-week OL period (Part 1) and the 4-week DB period (Part 2). Safety summary will be presented for each cohort in Part 1 and by treatment group in Part 2. Additionally, if any cohort has a the same linaclotide dose as the other cohorts, pooled summaries will also be provided.

The Baseline for safety analysis is defined as the last available measurement before the first study drug administration for each cohort, except the following:

- For subjects enrolled in 2 cohorts (Cohort 1 and Cohort 2; or Cohort 2 and Cohort 3), if subjects enroll into the next cohort within 28 days of last dose of the previous cohort, the baseline of the first cohort will be used the baseline for the second cohort.
- For subjects enrolled in all 3 cohorts (Cohort 1, Cohort 2, and Cohort 3), if subjects enroll into the second cohort and the third cohort within 28 days of last dose of the previous cohort, the baseline of Cohort 1 will be used the baseline for the second and third cohort.

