2.3 Treatment Assignment and Blinding

Approximately 30 subjects, 6 months to less than 2 years of age, will be sequentially enrolled into this study: six subjects in each cohort for Cohorts 1-3 and twelve subjects for

Part 2. Cohorts 1 to 3 will be open label with linaclotide only. Part 2 will be double blinded, and subjects will be randomized at a 1:1 ratio to linaclotide or placebo.

All cohorts will be of 7 to 12 weeks in duration: 0 to 4-week Screening Period (the minimal of 0 to 4-week period only applies to subjects that need wash out from prohibited medications), a 2 to 3-week Preintervention Period, followed by a 4-week Study Intervention Period, and a 1-week Postintervention Period.

In Part 1, linaclotide will be administered orally QD at the dose of 9 µg, 18 µg, and 36 µg for Cohort 1, Cohort 2 and Cohort 3, respectively. Part 2 will include additional subjects at the dose of linaclotide (either the 9, 18, or 36 µg dose) that exhibited the best benefit-risk profile from Part 1; and subjects receiving matching placebo.

In Cohorts 1-3, at least 5 subjects per cohort will need to complete treatment with an acceptable safety profile assessed by an internal Dose Escalation Review Committee which will give special attention to the presence of AESIs for the cohort to be declared safe to escalate to the next dose level.

In each cohort of Part 1, at least 1 subject will need to be \leq 12 months of age. The study investigator and the legally authorized representative (LAR)/parent/guardian will be given the option for the subject to continue in the next higher cohort (dose escalation) if the safety profile favors a trial cohort at a higher dose. Subjects who are participating in intrasubject dose escalation will need to repeat all screening procedures and eDiaries if > 30 days have elapsed since the subject's last dose in the previous cohort. Note: the screening number assigned by the Interactive response technology (IRT) at the initial screening visit should still be used. If symptoms have improved at the current dose level, the subject will be invited to participate in a long-term safety extension study once the study is active and accepting subjects. An internal Dose Escalation Review Committee will be monitoring the safety of Cohorts 1-3 and will provide a recommendation for the dose escalation to the next cohort or to stop the study based on the overall benefit-risk profile.

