Laboratory abnormalities will be evaluated based on Potentially Clinically Important (PCI) criteria ([Appendix C](#)). For each laboratory PCI criterion, the number and percentage of subjects who have a laboratory value meeting the criteria will be summarized by treatment group. Listings will be provided to summarize subject-level laboratory data for subjects meeting PCI criteria. The percentages will be calculated relative to the number of subjects with available non-PCI baseline values and at least 1 postbaseline assessment for the assessment period. The numerator will be the total number of subjects with available non-PCI baseline values and at least 1 PCI postbaseline assessment for the assessment Period. A supportive tabular display of subject with PCI postbaseline values will be provided.

Potential Hy's Law

Potential Hy's Law criteria within a 24-hour window is defined by a postbaseline elevation of ALT or AST $\geq 3 \times$ ULN, along with TBL $\geq 2 \times$ ULN and a non-elevated ALP $< 2 \times$ ULN, all based on blood draws collected within a 24-hour period.

Subjects who meet the potential Hy's Law criteria from the first dose of study drug to within 30 days after the last dose of treatment will be summarized. Supportive tabular displays will also be provided.

Assessment of Liver Enzyme and Bilirubin Elevations

The liver-specific laboratory tests include the serum glutamic pyruvic transaminase (SGPT/ALT), serum glutamic-oxaloacetic transaminase (SGOT/AST), alkaline phosphatase (ALP), and total bilirubin (TBL). The frequencies and percentages of subjects with post baseline liver specific function test values that meet the following criteria of potential clinical interest will be summarized by treatment group:

- ALT $\geq 3 \times$ ULN
- ALT $\geq 5 \times$ ULN
- ALT $\geq 10 \times$ ULN
- ALT $\geq 20 \times$ ULN
- AST $\geq 3 \times$ ULN
- AST $\geq 5 \times$ ULN
- AST $\geq 10 \times$ ULN
- AST $\geq 20 \times$ ULN
- TBL $\geq 2 \times$ ULN
- ALP $\geq 1.5 \times$ ULN
- ALT or AST $\geq 3 \times$ ULN
- ALT and/or AST $\geq 3 \times$ ULN and TBL $\geq 1.5 \times$ ULN
- ALT and/or AST $\geq 3 \times$ ULN and TBL $\geq 2 \times$ ULN
- ALT or AST $\geq 5 \times$ ULN for more than 2 weeks

- ALT or AST $\geq 8 \times$ ULN

where ULN is the upper normal limit. The maximum ratio relative to the ULN will be used to determine if subjects meet any of the criteria listed above.

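### SAP 10.1 carries the safety baseline forward only to day 28 while re-screening starts after day 30, so some roll-over children could get an on-drug lab and ECG baseline for the higher dose

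*SAP*

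**What the plan says.** SAP 10.1 gives a default: "The Baseline for safety analysis is defined as the last available measurement before the first study drug administration for each cohort". Two exceptions follow.

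- The first is addressed to a group: "For subjects enrolled in 2 cohorts (Cohort 1 and Cohort 2; or Cohort 2 and Cohort 3". It carries the first cohort's baseline forward "if subjects enroll into the next cohort within 28 days of last dose of the previous cohort".
- The second is for children in all three cohorts. It carries the Cohort 1 baseline to both later cohorts "if subjects enroll into the second cohort and the third cohort within 28 days of last dose of the previous cohort", so both gaps must be short.

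Re-screening runs on a different limit. SAP 2.3 has roll-over children "repeat all screening procedures and eDiaries if > 30 days have elapsed since the subject's last dose in the previous cohort". Protocol 4.1 and Operations Manual 2.1 give the same limit.

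Several summaries depend on this baseline. For PCI laboratory values, SAP 10.3 states: "The percentages will be calculated relative to the number of subjects with available non-PCI baseline values and at least 1 postbaseline assessment". SAP 10.5 applies the same restriction to ECG values. SAP 10.3 also counts CTC grade 3 and 4 laboratory values only if the grade is worse than at baseline, and its shift and change tables start from the same value.

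**The concern.** The two exceptions show the intent: a child who rolls over soon after dosing, without a fresh drug-free measurement, should still be compared with the drug-free value from before. The rule works only if every transition has either a carried baseline or a repeated screening. The two limits do not meet, and the three-cohort exception sets a joint condition on two separate transitions. Where neither exception nor re-screening applies, the default takes the last available value.

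For chemistry, hematology and ECG, that value is the end-of-treatment assessment at the lower dose. A change that arose at the lower dose and persists would then appear at the higher dose as no change, or would drop out of the PCI percentage. In cohorts of six, one child is enough to alter a table.

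**Working it through.** The plan gives no figure to reproduce; the check applies its rules to possible gaps.

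**Inputs**

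- Carry-forward limit: 28 days from last dose to entry into the next cohort (SAP 10.1).
- Re-screening: more than 30 days since last dose (SAP 2.3, Protocol 4.1, Operations Manual 2.1).
- Labs and ECG: scheduled at Screening (Visit 1) and Visit 5 only (Protocol Appendix D, Operations Manual 2.1). Visit 6 has vital signs but no lab or ECG (Operations Manual 2.2).
- Visit 5 timing: the optional PK sample is drawn with the clinical labs, before or after the last dose (Operations Manual 2.1, Week 4 notes). These values are therefore effectively on drug.
- Cohort size: 6 (SAP 2.3).

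**Step 1: two-cohort child.** Let g be the gap in whole days. The baseline is carried if g ≤ 28 and fresh if g > 30. It is neither if 28 < g ≤ 30. Over all gaps from 1 to 90 days, only g = 29 and g = 30 are uncovered (30 − 28 = 2 days).

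**Step 2: three-cohort child, literal reading.** The first exception does not apply, and the second needs g1 ≤ 28 and g2 ≤ 28. EOT means the end-of-treatment value.

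| g1 / g2 (days) | Cohort 2 lab/ECG baseline | Cohort 3 lab/ECG baseline |
|---|---|---|
| 10 / 10 | Cohort 1 baseline | Cohort 1 baseline |
| 10 / 45 | **Cohort 1 EOT** | re-screened |
| 45 / 10 | re-screened | **Cohort 2 EOT** |
| 10 / 29 | **Cohort 1 EOT** | **Cohort 2 EOT** |
| 29 / 10 | **Cohort 1 EOT** | **Cohort 2 EOT** |
| 45 / 45 | re-screened | re-screened |

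**Step 3: three-cohort child, pairwise reading.** If the first exception is applied to each adjacent pair of cohorts, Step 1 governs every transition and only days 29 and 30 remain uncovered.

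**Step 4: effect on a PCI percentage.** Suppose all six children have a post-baseline value, and one affected child has a PCI value at the lower dose's end of treatment that persists at the higher dose.

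- Drug-free (non-PCI) baseline: 1/6 = 16.7%.
- EOT (PCI) baseline: the child leaves numerator and denominator, giving 0/5 = 0%.
- With two events, one of them masked: 2/6 = 33.3% becomes 1/5 = 20.0%.

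**Step 5: one rule per transition.** If the baseline is carried whenever g ≤ 30 and fresh whenever g > 30, no gap from 1 to 90 days leaves an EOT value as baseline.

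**The case against.** A reader might infer that the rule hides an electrolyte or ECG signal from dose escalation. The documents do not support that. Protocol 4.1 and 5.11 rest escalation on adverse events, AESIs and committee review; TEAEs are defined by onset date (SAP 10.2.1) and AESIs by investigator or sponsor judgement (Protocol 6.1). None of these uses the SAP 10.1 baseline, and SAP 12.0 plans no interim analysis. The abnormality also still counts as post-baseline in the lower-dose cohort. SAP 10.3 and 10.5 add subject-level displays of PCI values, and SAP 5.0 lists children in more than one cohort. This objection stands and limits the point to the higher-dose summaries.

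The masking example also needs several conditions. Roll-over requires acceptable tolerability. The electrolyte PCI limits in SAP Table C-2 match Protocol Table 3, so an abnormality that is clinically significant, diarrhea-related and drug-related is an AESI and leads to discontinuation. Operations Manual 3.15 lists a repeat test among the responses to a clinically significant out-of-range value, and a repeat would replace the EOT value as last available. These points make the case uncommon, but do not exclude it: a PCI value need not be judged clinically significant, so it need be neither an AESI nor repeated.

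The three-cohort gap depends on reading. The first exception names adjacent pairs and speaks of the next and previous cohort, so it can be applied pairwise. Against that, chained pairwise use would make the second exception redundant. The wording is at best ambiguous, and days 29 and 30 stay open either way.

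**Conclusion.** The rule has a real gap with a narrow effect. On any reading, entry on day 29 or 30 yields neither a carried baseline nor a re-screened one. On the literal reading, so does a short-gap transition in a three-cohort child whose other gap exceeds 28 days. Gaps over 30 days are not affected, because screening is repeated.

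The consequence is confined to change from baseline, shift tables, CTC grade worsening and PCI percentages for labs and ECG in the higher-dose cohort. Scheduled vital signs and weight do not share the problem, since they are measured before dosing on Day 1 of each cohort.

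This assumes that both limits are counted in whole days from last dose to entry into the next cohort, and that no unscheduled or repeat test followed end of treatment. The 1/6 to 0/5 example further assumes a PCI value that persists. A reader might infer that much of a cohort could be affected. Nothing in the plan supports that: it forecasts no roll-over numbers, and affected children are only a subset of those who roll over. Few are likely; the number cannot be derived. The correction is still worth making, because the rule can return the kind of baseline its exceptions are there to avoid.

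**What to change.** Replace the two bullets in SAP 10.1 with one rule, applied to each transition separately:

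> If the child enters the next cohort 30 days or less after the last dose of the previous cohort (screening not repeated), the baseline used for the previous cohort is carried forward. If screening was repeated, the last measurement before first dose in the new cohort is the baseline.

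State also whether this covers vital signs and weight, as the current bullets do, or whether these use the pre-dose Day 1 value of each cohort. The choice matters for weight, which has percentage-change PCI criteria in SAP Table C-4.

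The 30-day limit is the protocol's own for re-screening, and the SAP already uses 30 days for TEAEs, deaths and Hy's Law.

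The cost is SAP wording and a small change to the baseline derivation, with no new data. The downside is a slightly older baseline for a few children: the limit at each transition moves by 30 − 28 = 2 days. A carried baseline also sets aside any later repeat test, as the present 28-day bullets already do.
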